#### 2. Study synopsis

The summary of the protocol is only available in German, and will thus not be copied in the SAP.

*Hypothesis*: The study hypothesis is that hemodynamic monitoring using hTEE in critically ill patients with hemodynamic compromise allows for an expedited reversal of circulatory impairment compared to standard ICU monitoring.

*Primary Objective:* To assess the impact of hemodynamic monitoring using the ImaCor ClariTEE technology on time to reversal of shock in hemodynamically compromised patients in comparison to standard monitoring.

Secondary Objective: To assess the safety and tolerability of the ImaCor ClariTEE probe.

*Study design*: Open-label, randomized controlled, single-centre trial. Subjects will be randomized into four groups in a two by two factorial study design. Assessed factors are the method of monitoring (use of hTEE monitoring vs. conventional monitoring) and the frequency of monitoring (use of per-protocol intervals for hemodynamic assessment vs. standard assessment intervals).

**Primary outcomes:** Time to resolution of hemodynamic instability defined as systemic mean blood pressure (MAP) > 60mmHg for at least 4 hours after discontinuation of vasopressors or inotropes. The criterion is considered fulfilled if >90% of MAP measurements occurring every 1-2 minutes is > 60mmHg for a 4 hour period.

**Secondary outcomes**: Time to death. Time to resolution of clinical signs of hypoperfusion as a composite of capillary refilling time < three seconds, urine output > 0.5 mL/kg/h for at least 4 hours, and blood lactate < 2 mmol/L. Use of pulmonary artery catheter (yes/no), central venous catheter (yes/no), or conventional echocardiography (yes/no). Occurrence of adverse events assumed to be due to prolonged hemodynamic impairment and treatment with vasopressors/inotropes (as binary yes/no outcomes): cardiac arrhythmias, excessive vasoconstriction, and secondary infections.

Please see the protocol (Version 4.0, January 2018) for a detailed description of the study.

CTU Bern	Statistical Analysis Plan ImaCorll	Date effective:	2018-04-24
	Based on CS_STA_TEM-11_SAPtemplate_v01		Page 6 I 16

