#### 6. Study endpoints

#### 6.1. Primary endpoints

The primary study outcome is the time from study inclusion to resolution of circulatory shock.

 Time to resolution of hemodynamic instability defined as systemic mean blood pressure (MAP) > 60mmHg for at least 4 hours after discontinuation vasopressors or inotropes (dobutamine, milrinone, norepinephrine or epinephrine). The criterion is considered fulfilled if >90% of MAP measurements (occurring every 1 - 2 minutes) is > 60mmHg for a 4 hour period.

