#### 6.2. Secondary endpoints

• Time to death

CTU Bern	Statistical Analysis Plan ImaCorII	Date effective:	2018-04-24	
	Based on CS_STA_TEM-11_SAPtemplate_v01			Page 8 I 16

- Time to resolution of clinical signs of hypoperfusion as a composite of capillary refilling time < three seconds, urine output > 0.5 mL/kg/h for at least 4 hours, and blood lactate < 2 mmol/L.
- Use of conventional hemodynamic monitoring (3 binary endpoints):
  - o pulmonary artery catheter (yes/no),
  - o central venous catheter (yes/no),
  - conventional echocardiography (yes/no)
- Occurrence of adverse events assumed to be due to prolonged hemodynamic impairment and treatment with vasopressors/inotropes (as binary yes/no outcomes):
  - cardiac arrhythmias: non sustained ventricular tachycardia (≥ 4 beats), sustained ventricular tachycardia, ventricular fibrillation, atrial fibrillation, atrial flutter, other supraventricular tachycardia, new onset AV block (I/II/III), or asystole,
  - Excessive vasoconstriction: occurrence of acute myocardial infarction, skin necrosis, or secondary bowel or limb ischemia or stroke,
  - Secondary infections (catheter related infections, VAP, new onset of sepsis).

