#### 7.3. Data preparation

The primary endpoint will be derived as the difference in hours between the date and time of randomization and the date and time of resolution of clinical shock. The competing risk of death for the primary outcome will be derived as the difference in hours between the date and time of randomization and the date and time of discontinuation of therapy before death.

Secondary and further endpoints will be derived as follows:

- Time to death (in hours) will be derived as the difference in hours from randomization to discontinuation of therapy before death.
- Time to resolution of clinical signs of shock will be derived as the difference in hours from randomisation to the latest time of any of the three: first lactate below 2 mmol/L, urine output above 0.5 ml/kg body weight or first capillary refilling time below three seconds
- Pulmonary artery catheter is yes if it was yes during any assessment
- Central venous catheter is yes if it was yes during any assessment
- Conventional echocardiography will be regarded as yes if TEE or TTE was used during any assessment
- Cardiac arrhythmias will be derived from any non sustained ventricular tachycardia (≥ 4 beats), sustained ventricular tachycardia, ventricular fibrillation, atrial fibrillation, atrial flutter, other supraventricular tachycardia, new onset AV block (I/II/III), or asystole
- myocardial infarction, skin necrosis, and stroke will be taken as is
- secondary bowel or limb ischemia will be derived from any bowel ischemia or any limb ischemia
- secondary infections will be derived from any catheter infection, VAP infection or sepsis
- Length of time with organ support (in hours) will be derived from length of time with mechanical ventilation and/or renal replacement therapy. If a patient received both, times will be added. If therapies are overlapping, time will only be counted once.
- Length of time in ICU (in hours) will be taken from eCRF as is.
- Length of time in hospital (in hours) will be taken from eCRF as is.

CTU Bern			2018-04-24
CTO Bern	Based on CS_STA_TEM-11_SAPtemplate_v01		Page 10 I 16

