#### Primary analysis of secondary endpoints

The secondary outcome time to death will be evaluated using Cox proportional-hazards regression. Other secondary time-to-event outcomes will be analysed using competing risk models as described above. Binary outcomes will be analysed using logistic regression, All models will be adjusted for the frequency of monitoring (protocolled vs standard).

CTU Bern	Statistical Analysis Plan ImaCorll	Date effective: 2018-04-24		
CTO Bern	Based on CS_STA_TEM-11_SAPtemplate_v01			Page 13 I 16

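### Section 7.3 dates resolution of hypoperfusion at the latest of separately determined times, without requiring the signs that normalised earlier to be still normal then

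*SAP*

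**What the plan says.** Section 6.2 defines the secondary endpoint as "Time to resolution of clinical signs of hypoperfusion as a composite of capillary refilling time < three seconds", together with a urine and a lactate criterion. The synopsis in section 2 has the same composite and joins its parts with *and*: "urine output > 0.5 mL/kg/h for at least 4 hours, and blood lactate < 2 mmol/L".

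Section 7.3 turns this into a date, counted from randomisation: "the latest time of any of the three: first lactate below 2 mmol/L, urine output above 0.5 ml/kg body weight". The remaining sign enters in the same way, by the "first capillary refilling time below three seconds". The word *first* is attached to lactate and to capillary refill, but not to urine output.

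The derived date is the event time in the model. Section 9.5.1, under the primary analysis of secondary endpoints, states: "Other secondary time-to-event outcomes will be analysed using competing risk models as described above".

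No other section requires the three signs to be normal at the same assessment, or says what happens when a sign becomes abnormal again.

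**The concern.** Resolution of a composite joined by *and* is naturally read as a state in which all three signs are normal. The latest of three separate times does not establish that state. It establishes only that each sign has been normal at some point up to then.

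The two coincide when signs stay normal once they have normalised. They part when lactate or capillary refill normalises, worsens again, and is abnormal when the last sign first meets its criterion. That patient is entered as resolved while still showing a sign of hypoperfusion.

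The error runs in one direction, since the date can be too early but never too late. It arises even with identical assessment schedules in all four groups, so it reaches the hTEE comparison as well as the frequency comparison. At stake is whether the endpoint measures what its name says, and whether a difference between groups in relapse before joint recovery would show.

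**Working it through.** The SAP gives no figure for this endpoint, so there is none to reproduce. The check has a logical part, which is certain, and an illustrative part, which rests on assumptions.

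**1. The two dates.**
- Rule time (section 7.3) = max(first time lactate < 2 mmol/L, time urine criterion met, first time capillary refill < 3 s).
- Joint time = first assessment at which all three hold together.

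At the joint time each sign is normal, so its own first normal time is no later. Hence rule time ≤ joint time always. They are equal only if no sign that normalised earlier is abnormal again at the rule time.

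**2. A constructed patient (invented values, assessed every 4 h).** Urine output is judged here by single readings, as section 7.3 words it.

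| Hours | 0 | 4 | 8 | 12 | 16 | 20 | 24 |
|---|---|---|---|---|---|---|---|
| Lactate (mmol/L) | 4 | 1.8 | 3 | 3.2 | 2.8 | 1.9 | 1.5 |
| Urine output (mL/kg/h) | 0.2 | 0.3 | 0.7 | 0.3 | 0.4 | 0.8 | 0.9 |
| Capillary refill (s) | 5 | 4 | 4 | 2 | 4 | 2 | 2 |

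First normal times are 4 h, 8 h and 12 h, so the rule time is max(4, 8, 12) = 12 h. At 12 h lactate is 3.2 and urine output 0.3, both abnormal. The joint time is 20 h, so the event is dated 20 − 12 = 8 h early. Had follow-up ended at 16 h, the three signs would never have been normal together, yet the patient would count as resolved at 12 h.

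**3. How often, under assumptions.** None of these inputs comes from the SAP: three independent signs, readings every 4 h for 6 days, and a 25% chance per reading that an abnormal sign normalises. The chance per reading that a normal sign relapses is varied. There are 20,000 simulated patients and no deaths.

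- Dated before joint normality: 0%, about 9%, 20% and 35% at relapse of 0%, 2%, 5% and 10% per reading; 54% and 67% at 20% and 30%.
- Counted as resolved but never jointly normal within 6 days: 0%, 0.1%, 0.7%, 3.7% and 9.4% at relapse of 0%, 5%, 10%, 20% and 30%.
- Median rule time: 24 h throughout. Median joint time among those who reached it: 24, 28, 28, 36 and 44 h at the same five relapse rates.

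**4. Effect on a between-arm comparison, in the same model (relapse 2%, 5%, 10%).**
- One arm normalises faster (0.33 instead of 0.25 per reading): hazard ratio 1.50, 1.47 and 1.46 under the section 7.3 rule, against 1.50 under joint normality. The level of these ratios depends on how ties on the 4-hour grid are handled; the closeness of the two rules is what matters.
- One arm has half the relapse rate: about 1.0 under the section 7.3 rule, against 1.04, 1.12 and 1.22 under joint normality.

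**The case against.** The strongest reply is that section 7.3 does not contradict section 6.2 on this point. Section 6.2 does not say that the signs must be normal simultaneously, and the rule honours the *and* by waiting for all three. That is fair as to the wording, and concurrency is a reading rather than a quotation. It does not rescue the rule: a patient whose lactate is abnormal again does not meet a composite that includes normal lactate, and section 7.3 can date resolution at that moment. Section 8.2.2 also judges the same three signs together at screening when it describes a patient without hypoperfusion.

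Other limits stand:
- *First* is literal for only two of the three signs. Two are enough for the defect.
- Section 7.3 does not say whether values at entry count. A reader might infer that a sign normal at entry is fixed as resolved from time zero; the text leaves this open.
- A reader might infer that the endpoint fails to capture sustained recovery. It was not defined to do so: section 6.2 asks for persistence only of urine output, unlike the primary endpoint, whose MAP criterion "is > 60mmHg for a 4 hour period". Dating by joint normality would not measure sustained recovery either. The misdating concerns only relapses before the last sign first normalises.
- A reader might infer that the treatment comparison is invalid. The figures do not support that. The hypothesis in section 5 is faster reversal, and in that scenario the two rules nearly agree.
- The SAP does not show whether readings of all three signs continued after the first normal value. Sections 7.3 and 9.4 refer to repeated assessments, which suggests serial data but does not prove it.

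**Conclusion.** The point holds in a limited form. As written, section 7.3 gives too early an event time for any patient whose lactate or capillary refill relapses before the last sign normalises and is abnormal when it does. In rare cases it credits resolution that never occurred jointly. That follows from the rule itself and needs no assumption.

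The size does rest on assumptions: the 9% to 35% range depends wholly on the assumed relapse and normalisation rates, the 4-hour grid and independence of the signs. With no relapse the problem vanishes. Crediting resolution without any joint normality is uncommon, at 0.7% or less for relapse up to 10% per reading.

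One secondary endpoint is affected and the primary endpoint is untouched. The rule can mask a difference between groups in early relapse, but it does not rule out finding one. If monitoring mainly speeds normalisation, the distortion of the comparison is likely small. The change is worth making because it is specific and cheap.

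**What to change.** In section 7.3, define the event as the first assessment after randomisation at which all three section 6.2 criteria hold together, with urine output as defined there, including its rate per hour and 4-hour duration. Use the most recent value of each sign, state the maximum age at which a value may still be carried forward, and state whether values at entry count. Keep the present rule as a sensitivity analysis.

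If values after the first normal reading were not recorded, joint dating is impossible. Then keep the rule and relabel the endpoint as time until each sign has been normal at least once.

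The cost is a change of wording and one re-derivation if the serial data exist. The downsides are somewhat later event times, a few more censored patients, and a carry-forward rule that has to be specified.

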#### 8.2.2. Per-protocol (PP)

The per-protocol population consists of all subjects in the FAS who did not have any protocol deviations during follow up that could confound the interpretation of analyses conducted on the FAS. The following are common major protocol deviations:

- General protocol violations:
  - No hemodynamic instability at screening (i.e.  $MAP \ge 60 \text{ mmHg}$ )
  - No signs of hypoperfusion or organ dysfunction at screening (i.e. capillary refilling time < 3 seconds, urine output  $\geq$  0.5 ml/kg/h, lactate  $\leq$  2 mmol/l)
  - $\circ$   $\,$  Oesophageal conditions not allowing use of TEE, i.e.
    - Unrepaired tracheoesophageal fistula
    - Prior oesophageal or gastric surgery
    - Oesophageal obstruction or stricture
    - Oesophageal varices or diverticulum
    - Gastric or oesophageal bleeding
    - Recent oesophageal surgery
- Protocol violations in monitoring method:
  - Use of hTEE in conventional monitoring arms and vice versa
- Protocol violations in monitoring interval:
  - Mean interval among monitoring shorter than 6 h for the standard interval arms, and longer than 6 hours for the per-protocol interval arms.

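### The derivation rule in SAP section 7.3 drops the 4-hour duration and the hourly unit from the urine part of the hypoperfusion endpoint, so its event time can differ from the one section 6.2 defines

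*SAP*

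**What the plan says.** The endpoint is defined twice, in the same terms. The synopsis (section 2) has "capillary refilling time < three seconds, urine output > 0.5 mL/kg/h for at least 4 hours", with a lactate criterion following. Section 6.2 has "urine output > 0.5 mL/kg/h for at least 4 hours, and blood lactate < 2 mmol/L", with the same refill criterion before it. In both places the urine criterion has three parts: a threshold, a per-hour unit and a minimum duration.

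Section 7.3 then gives the calculation. It opens with "Time to resolution of clinical signs of shock will be derived as the difference in hours", counted from randomisation to the "latest time of any of the three: first lactate below 2 mmol/L, urine output above 0.5 ml/kg body weight", and the third element is the first refill time under three seconds. The urine element there keeps only the threshold per kilogram.

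Under the analysis of secondary endpoints in section 9.5.1 the SAP says: "Other secondary time-to-event outcomes will be analysed using competing risk models as described above". Section 9.5.2 applies the same analyses to the frequency comparison. The derived time therefore enters models for both factors.

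The table of deviations in section 10 has no entry on the components of this endpoint.

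**The concern.** Section 7.3 is the section from which the variable will be programmed. If its urine rule is looser than the definition, a brief rise in output can satisfy the criterion in a patient whom section 6.2 would still count as unresolved. Two analysts, one working from 6.2 and the other from 7.3, could then obtain different event times for the same patient.

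The consequence is limited to one component of one secondary endpoint. That endpoint is nevertheless tested by regression in both factor comparisons, so its event time should have a single definition.

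**Working it through.** The SAP gives no figure to reproduce here. The check is a comparison of the sections, followed by simple arithmetic on what the difference can do.

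**Step 1. The components side by side.**

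| Component | Sections 2 and 6.2 | Section 7.3 |
|---|---|---|
| Lactate | below 2 mmol/L | first value below 2 mmol/L |
| Capillary refill | below 3 s | first value below 3 s |
| Urine: threshold | above 0.5 mL/kg | above 0.5 mL/kg |
| Urine: unit of time | per hour | not given |
| Urine: duration | at least 4 h | not given |
| Urine: which time point | not given | not given |

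The lactate and refill thresholds agree. Only the urine criterion loses something.

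**Step 2. Does another section restore what is missing?** For the unit, in effect yes: the list of violations in section 8.2.2 uses "0.5 ml/kg/h, lactate", so the hourly rate is evidently meant. For the duration, no other section brings it into the derivation, and section 10 does not declare its removal.

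**Step 3. The time point.** In 7.3 the word for the earliest value stands before lactate and again before refill, but not before urine. The urine time is therefore underspecified. Taking the first rise is one reading of the rule, not the only one.

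**Step 4. Size without relapse, unit read as hourly.** Let u, l and r be the hours at which urine, lactate and refill become normal and stay so.

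- Section 7.3: T = max(u, l, r).
- Section 6.2, event at the start of the window: T = max(u, l, r). Shift = 0.
- Section 6.2, event at the end of the window: T = max(u + 4, l, r). Shift = max(0, u + 4 − max(u, l, r)).

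With u = 10 (values chosen for illustration):

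| l = r | 7.3 | 6.2, start | 6.2, end | Shift (start / end) |
|---|---|---|---|---|
| 6 | 10 | 10 | 14 | 0 / 4 h |
| 12 | 12 | 12 | 14 | 0 / 2 h |
| 15 | 15 | 15 | 15 | 0 / 0 h |

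The shift is 4 h at most, when urine is the last sign to normalise. It is 0 h when lactate or refill turns normal 4 h or more after urine.

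**Step 5. Size with relapse.** Take an assumed patient whose urine output is above threshold for 1 h at hour 6, then below it until hour 20, then sustained. Lactate and refill are normal from hour 10 and stay so.

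- Section 7.3, if the first rise is taken: max(6, 10, 10) = 10 h.
- Section 6.2: max(20, 10, 10) = 20 h (start) or max(24, 10, 10) = 24 h (end).

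On that reading the difference is 20 − 10 = 10 h or 24 − 10 = 14 h. The patient is invented and shows only that the shift can exceed 4 h. The SAP gives no relapse rate and no component-level data, so neither the frequency nor the average size of such shifts can be calculated.

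**The case against.** The best reply is that 7.3 is shorthand. The full definition stands twice elsewhere, the missing unit and the missing duration sit in the same clause, and if one is a slip the other may be too. Section 7.3 also leaves things to section 6 in another place: its primary-endpoint line refers only to "the date and time of resolution of clinical shock" and leaves to section 6.1 the rule that pressure "is > 60mmHg for a 4 hour period". The absence of the word for the earliest value before urine could mean that urine is timed by its own 4-hour rule.

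This has weight, and it is why the claim is only that an unsustained rise can count. It does not remove the discrepancy. The primary-endpoint line restates no threshold and so must be completed from 6.1. The hypoperfusion rule restates all three thresholds, adds its own way of combining them and does not refer back, so it can be programmed as it stands.

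A second reply is that the database may already hold a sustained-urine time. That is possible, but the SAP does not say so. Where 7.3 takes a recorded value unchanged, as for length of stay, it states this.

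Two stronger readings are tempting. A reader might infer that taking the latest of three separate times is itself an error, because a sign may have relapsed by then, or that the slightly different endpoint name in 7.3 signals a different endpoint. The document supports neither. Section 6.2 does not say whether the signs must hold together, 7.3 gives a clear rule, and no other secondary endpoint could be meant by that name.

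**Conclusion.** The discrepancy is real: the derivation in 7.3 omits the 4-hour duration that the definition requires, and nothing in the SAP restores it or declares the change. The hourly unit is also missing, probably by oversight, and the urine time point is not fixed.

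The effect is confined to patients in whom sustained urine output comes later than both other signs. If no sign relapses, the limits are those of step 4, with 4 h as the maximum. Beyond that, any estimate would rest on relapse rates that the SAP does not give.

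A reader might infer that the hTEE comparison is biased or that the main result is at risk. The document does not support this. The rule is the same in every arm, and neither the primary endpoint nor the sample size uses this variable. It should be corrected before analysis, as a specific and inexpensive repair to a secondary endpoint.

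**What to change.** Reconcile sections 2, 6.2 and 7.3 before the endpoint is derived:

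1. In 7.3, apply to urine the same hourly unit and 4-hour duration as in 6.2.
2. State whether the start or the end of the 4-hour window is the event time.
3. If the looser rule in 7.3 is intended and departs from the protocol, list it in section 10 with a reason.

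The cost is a few words in the SAP and one derivation step. If the database holds only a single recorded urine time and not serial values, the SAP should say which time that is.

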#### 9.2. Demographics and baseline characteristics

The patient characteristics of the FAS at baseline will be presented in a table, stratified by the four intervention arms (defined by both methods and both frequencies of hemodynamic monitoring), as number and percentage for categorical and mean and standard deviation for continuous variables. For data severely deviating from a normal distribution, we will present median and interquartile ranges. No statistical comparisons of patient characteristics at baseline will be performed. The following variables will be considered:

- Age
- Gender
- Weight
- Height
- Patient admission from: emergency department, ward, external ICU, coronary laboratory, op, and other
- Admission diagnosis: cardiovascular, gastrointestinal, metabolic, neurological, renal or genitourinary, respiratory, trauma, infectious
- Comorbidities: septic shock, chronic lung disease, chronic cardiovascular disease, chronic liver disease, chronic renal failure, immunosuppression, lymphoma, metastatic cancer, leukaemia or myeloma,
- Apache II score,
- SAPS II score, and
- SOFA score.

CTU Bern	Statistical Analysis Plan ImaCorII	Date effective: 2018-04-24		
	Based on CS_STA_TEM-11_SAPtemplate_v01			Page 12 I 16

UNIVERSITÄT BERN

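### The section 7.3 derivations of secondary infection and of bowel or limb ischaemia are wider than the section 6.2 definitions and can count conditions already present at randomisation

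*SAP*

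**What the plan says.** Section 6.2 introduces a group of binary secondary endpoints as "Occurrence of adverse events assumed to be due to prolonged hemodynamic impairment and treatment with vasopressors/inotropes". Two of its three composites carry limits that matter here:

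- Infection: "Secondary infections (catheter related infections, VAP, new onset of sepsis".
- Vasoconstriction: "Excessive vasoconstriction: occurrence of acute myocardial infarction, skin necrosis, or secondary bowel or limb ischemia or stroke".

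Section 7.3 gives the derivations:

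- Infection: "secondary infections will be derived from any catheter infection, VAP infection or sepsis".
- Bowel or limb ischaemia: "secondary bowel or limb ischemia will be derived from any bowel ischemia or any limb ischemia".
- Other vasoconstriction components: "myocardial infarction, skin necrosis, and stroke will be taken as is".

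Section 9.2 includes this item in the baseline table: "Comorbidities: septic shock, chronic lung disease, chronic cardiovascular disease". It also lists an infectious category among the admission diagnoses.

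Under sections 9.5.1 and 9.5.2 the binary outcomes go into logistic regression, adjusted only for the other randomised factor. Section 10 records that the adverse-event composites were defined in the SAP because the protocol listed the events without combining them.

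**The concern.** Section 7.3 is the text from which the endpoint is programmed. Followed literally, it drops the new-onset limit on sepsis and replaces secondary ischaemia with any ischaemia. A patient randomised while in septic shock could then be scored as having a secondary infection, although nothing done after randomisation could have caused or prevented it.

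Such cases raise the event rate in every arm and carry no information on the monitoring strategy. They shrink the contrast that the logistic model estimates. The model does not adjust for baseline sepsis, so a chance imbalance in it would also add noise to the estimate.

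**Working it through.** **Side-by-side comparison of 6.2 and 7.3**

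| Component | Limit in 6.2 | Rule in 7.3 | Limit lost? |
|---|---|---|---|
| Sepsis | new onset | sepsis, unqualified | yes |
| Bowel or limb ischaemia | secondary | any (secondary stays in the label only) | yes, in the rule |
| Myocardial infarction | acute | taken as recorded | acute is lost |
| Stroke | at most an ambiguous carry-over of secondary | taken as recorded | unclear |
| Atrial fibrillation, flutter | none | none | no |
| AV block | new onset | new onset | no |

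The last two rows come from the arrhythmia list, which has the same content in both sections: "atrial fibrillation, atrial flutter, other supraventricular tachycardia, new onset AV block (I/II/III), or asystole". Section 7.3 keeps the new-onset limit for AV block, so an analyst could reasonably read its absence for sepsis as intended.

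**Is there an onset rule elsewhere?** The only one is the treatment-emergent definition in section 9.7, and it covers SAEs only. Section 7.1 says that the database was built without validation or error checks, so a safeguard at data entry cannot be presumed.

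**Size, as illustration only.** The plan states no figure to reproduce. The only input from the SAP is the sample size in section 4.2: 125 per group, so 2 × 125 = 250 per monitoring method. The event risks and the prevalence are assumptions.

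Let b be the share of patients in whom the condition is already present and is recorded as an event, and p the new-onset risk among the rest. Then:

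- Recorded risk = b + (1 − b) × p.
- Recorded risk difference = (1 − b) × (p₁ − p₂).
- Odds ratio = [r₂/(1 − r₂)] / [r₁/(1 − r₁)], where r₁ and r₂ are the recorded risks.

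Assume p₁ = 20% and p₂ = 12%. With b = 20%, r₁ = 0.20 + 0.80 × 0.20 = 0.360 and r₂ = 0.20 + 0.80 × 0.12 = 0.296. The odds ratio is (0.296/0.704) / (0.360/0.640) = 0.75. Power is for a two-sided 5% comparison of two proportions.

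| b | Recorded risks | Odds ratio | Power |
|---|---|---|---|
| 0% | 20.0% vs 12.0% | 0.55 | 69% |
| 10% | 28.0% vs 20.8% | 0.68 | 47% |
| 20% | 36.0% vs 29.6% | 0.75 | 33% |
| 30% | 44.0% vs 38.4% | 0.79 | 25% |
| 50% | 60.0% vs 56.0% | 0.85 | 15% |

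A smaller assumed effect, 15% versus 10%, gives the same pattern. The odds ratio, with the higher-risk arm in the numerator, falls from 1.59 to 1.21, 1.16 and 1.13 at b = 20%, 30% and 40%. Power falls from 39% to 16%, 12% and 10%.

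**The case against.** The best defence is that section 7.3 only says which recorded items are combined. On that reading, any means that either item is positive, the endpoint name still carries secondary, and the inputs are the adverse events listed in the protocol. Septic shock at entry is a separate baseline item, and nothing shows that the sepsis item in 7.3 draws on it. This stands to the extent that the data fields are not shown and may hold only events during the study. It does not remove the conflict in the text: for sepsis the limit is absent from both the label and the rule.

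Some stronger readings are tempting, but the document does not support them:

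- *Septic patients will be counted as complications.* The text permits this. It does not establish it.
- *Section 7.3 also dropped a limit on atrial fibrillation.* Section 6.2 never set one, so any gap lies in the definition itself.
- *Infarction lost a new-onset limit.* It lost only acute, and restoring that word would not exclude an acute infarction that caused the shock.
- *The comparison is biased towards one arm.* Randomisation balances pre-existing cases in expectation. The consequence is dilution, and chance imbalance is reflected in the confidence interval.
- *The baseline table can identify all prevalent cases.* Section 9.2 names septic shock. For atrial fibrillation, infarction, stroke and ischaemia it has only broad categories, and excluding patients on those would discard true new events.

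It is also fair to say that these comparisons may be weak in any case: power is 39% under the smaller assumed effect even with no prevalent cases.

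**Conclusion.** The point holds for sepsis and for bowel or limb ischaemia, where the derivation in 7.3 is wider than the definition in 6.2. Sepsis is the clearer case, because the SAP itself expects septic shock at baseline. Infarction has a smaller mismatch, the missing word acute.

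The loss cannot be quantified from the SAP. The figures above assume the event risks and the prevalence, and they also assume that every prevalent case is recorded as an event, which is the open question. The direction, towards no difference, does not depend on the particular rates chosen.

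Only secondary endpoints are touched, and the primary endpoint and its analysis are unaffected. Because these endpoints are compared inferentially, the derivation should be corrected before the final analysis.

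**What to change.** Change section 7.3 as follows:

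- Count sepsis only if it is of new onset after randomisation. A patient with septic shock at baseline counts only for a new episode, a catheter infection or VAP.
- Count bowel or limb ischaemia only if its onset is after randomisation.
- Restore acute for myocardial infarction.
- Resolve unclear onset through the data queries already provided for in section 7.2. Use the baseline septic shock field for sepsis only.

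As a separate point, state in both 6.2 and 7.3 whether arrhythmias, infarction and stroke must also begin after randomisation, and apply that condition only where the database records onset. This would add to the 6.2 definitions, not restore them. Since the trial is open-label and the statistician unblinded, the change should be dated and recorded before the final analysis.

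The cost is a few lines of SAP text, some programming and some onset queries. The downside is lower event counts.
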